8.2.6 Viral serology

Viral serology screening will be performed using a commercially available kit at the times given in the SoA (Section 1.3).

Page 82 of 133 Version: 7.0 Date: 09 FEB 2023

The screen will test for hepatitis B core antibodies (anti-HBc), hepatitis B surface antigens (HBsAg), hepatitis surface antibodies (anti-HBs), HCV antibodies (anti-HCV). Additionally, HIV (1/2) testing is required if the patient has never been tested for HIV, or if testing was done prior to primary cancer diagnosis or performed ≥ 12 months prior to trial start.

8.2.7 Safety follow-up (SFU1 and SFU2)

Patients will be followed-up for safety assessments at two safety follow-up visits (SFU1 and SFU2) after last treatment, where all AEs and concomitant medications must be reported. If the patient is not able to attend the clinic due to his/her clinical condition, a phone call should be done to assess possible AEs.

The first safety follow-up visit (SFU1) takes place 30 (+ 5) days after last treatment and the second safety follow-up visit (SFU2) takes place 90 (±7) days after last treatment.

8.3 Adverse events and serious adverse events

The investigator and any qualified designees are responsible for detecting, documenting, and recording events that meet the definition of an AE or SAE and remain responsible for following up all AEs and SAEs.

8.3.1 Time period and frequency for collecting adverse event and serious adverse event information

All AEs and SAEs will be collected from the first signing of the ICF until the SFU2 visit (90 days after last trial dose or until a new anti-cancer therapy is started) at the time points specified in the SoA (Section 1.3). Additionally, in case a new anti-cancer therapy is started within 90 days after last treatment, the safety follow-up visit should be performed just prior to starting the new anti-cancer therapy. Adverse events after start of new anti-cancer therapy do not need to be reported unless a causal relationship to BNT111-01 or cemiplimab is suspected.

All SAEs (initial and follow-up reports) will be recorded and reported to the sponsor or designee within the appropriate time frame and under no circumstance should this exceed 24 h after knowledge of the event, as indicated in Section 10.3.1.10. AESIs should also be reported within an appropriate time frame (i.e., no more than 24 h after knowledge of the event).

Investigators are not obligated to actively seek AEs or SAEs after a patient has discontinued from the trial. However, if the investigator learns of any SAE, including a death, at any time after a patient has discontinued from the trial, and he/she considers the event to be reasonably related to the trial treatment or trial participation, the investigator must promptly notify the sponsor.

8.3.2 Method of detecting adverse events and serious adverse events

The method of recording, evaluating, and assessing causality of AEs and SAEs and the procedures for completing and transmitting SAE reports are provided in Section 10.3.

Page 83 of 133 Version: 7.0 Date: 09 FEB 2023

Care will be taken not to introduce bias when detecting AEs and/or SAEs. Open-ended and non-leading verbal questioning of the patient is the preferred method to inquire about AE occurrences.

8.3.3 Follow-up of AEs and SAEs

After the initial AE/SAE report, the investigator is required to proactively follow each patient at subsequent visits/contacts. All AEs/SAEs will be followed until resolution, stabilization, the event is otherwise explained, or the patient is lost to follow-up (as defined in Section 7.3). Further information on follow-up procedures is provided in Section 10.3.1.7.

The investigator is obligated to perform or arrange for the conduct of supplemental measurements and/or evaluations as medically indicated or as requested by the sponsor to elucidate the nature and/or causality of the AE or SAE as fully as possible. This may include additional laboratory tests or investigations, histopathological examinations, or consultation with other health care professionals.

If a patient dies during participation in the trial or during the 90-day safety follow-up period, the investigator will provide the sponsor with a copy of any post mortem findings including histopathology.

New or updated information will be recorded in the originally completed eCRF.

The investigator will submit any updated SAE data to the sponsor within 24 h of receipt of the information.

All ongoing AEs/SAEs will be followed until resolution, considered by the investigator to be stable or chronic (resolved with sequelae), the patient is lost to follow-up or the patient withdraws consent. If no final status is reached at SFU2 (90 days after last trial treatment), the investigator must confirm the unavailability of a final status.

8.3.4 Regulatory reporting requirements for SAEs

Prompt notification of an SAE by the investigator to the sponsor is essential so that legal obligations and ethical responsibilities towards the safety of patients and the safety of a trial treatment under clinical investigation are met.

The sponsor has a legal responsibility to notify both the local regulatory authority and other regulatory agencies about the safety of a trial treatment under clinical investigation. The sponsor will comply with country-specific regulatory requirements relating to safety reporting to the regulatory authority, institutional review boards (IRBs)/independent ethics committees (IECs), and investigators. The execution of expedited reporting to the different entities may be delegated as detailed in the trial-specific Safety Management Plan.

Safety reports will be prepared for SUSARs according to local regulatory requirements and sponsor policy and forwarded to investigators as necessary.

For events related to IMPs, it is the sponsor's or delegate's responsibility to perform SUSAR reporting to the regulatory authority, the IRB/IEC and the other investigators as required by national law and applicable guidelines.

Page 84 of 133 Version: 7.0 Date: 09 FEB 2023

An investigator who receives an investigator safety report describing an SAE or other specific safety information (e.g., summary or listing of SAEs) from the sponsor should review it and then file it together with the IB. If required by local requirements, the investigator will notify the relevant IRB/IEC.

8.3.5 Pregnancy

Pregnant and breastfeeding women are excluded from participation in the trial. Any WOCBP must have a negative pregnancy test (beta-HCG) at baseline and be willing to use highly effective methods of contraception (less than 1% of unintended pregnancies per year, according to ICH M3) for the duration of trial treatment until 6 months after the last administration of the trial drug. Male patients must use an accepted contraceptive method for the duration of trial treatment and at least 6 months after the last administration of the trial drug.

If a pregnancy occurs during the trial and within 90 days after the last trial treatment, the investigator should inform the sponsor within 24 h of knowledge of the pregnancy and should follow the procedures outlined in Section 10.4.

Abnormal pregnancy outcomes (e.g., spontaneous abortion, fetal death, stillbirth, congenital anomalies, ectopic pregnancy) are considered SAEs.

8.3.6 Death events

Any death that occurs within the observation period (from the first signing of the ICF until 90 d after the last trial dose) will be reported as an SAE. A copy of an autopsy report should be submitted if available upon request. Date and cause of death will be recorded.

In case of a fatal event, the event term should not be "death" but the underlying event which led to death (death = outcome). If there is more than one AE in a fatal case, only for the AE leading to death the outcome "fatal" should be selected. If the cause of death is unknown and cannot be ascertained at the time of reporting, the most likely reason for death should be documented as event term.

Deaths due to disease progression occurring within 90 days of the last trial treatment must be reported as a Grade 5 SAE. The AE term on the SAE form should be reported as "disease progression" of the disease under trial treatment, i.e., "progression of advanced/metastatic melanoma". All deaths due to disease progression occurring after 90 days from the end of trial treatment will be reported on the trial-specific death page of the eCRF.

8.3.7 Disease-related events and/or disease-related outcomes not qualifying as AEs or SAEs

Non-fatal events that are clearly consistent with the expected pattern of progression of the underlying disease (e.g., new metastases) should **not** be recorded as AEs. These data will be captured as efficacy assessment data only and will be recorded on the tumor response evaluation pages in the eCRF. In most cases, the expected pattern of progression will be based on RECIST 1.1. In rare cases, the determination of clinical progression will be

Page 85 of 133 Version: 7.0 Date: 09 FEB 2023

based on symptomatic deterioration; however, every effort should be made to document progression using objective criteria.

If there is any uncertainty as to whether an event is due to disease progression, it should be reported as an AE.

Note: Symptoms resulting from the progression and clearly stated as related to the PD will not be documented as AEs nor reported as SAEs. However, specific symptoms at time of progression that may be caused by other reason and death due to disease progression, will have to be documented as AEs and reported as SAEs if applicable.

8.3.8 Immune-related adverse events

irAEs are defined in Appendix 12.1. The investigators are asked to pay special attention to the detection and reporting of irAEs and their relationship to either of the treatments.

8.4 Adverse events of special interest

An AESI, serious or non-serious, is one of scientific and medical concern specific to the sponsor's product or program, for which ongoing monitoring and rapid communication by the investigator to the sponsor are appropriate. Such an event might warrant further investigation in order to characterize and understand it. Depending on the nature of the event, rapid communication by the trial sponsor to other parties (e.g., regulators) might also be warranted.

The following AEs should be reported if related to cemiplimab:

- Grade ≥ 2 infusion-related reactions are considered AESIs and must be reported within 24 h of identification by the investigator.
- Grade ≥ 3 irAEs are considered AESIs and should be reported within 24 h of identification by the investigator.

Note: An irAE can occur shortly after the first dose or several months after the last dose of treatment. All AEs of unknown etiology associated with drug exposure should be evaluated to determine possible immune etiology. If an irAE is suspected, efforts should be made to rule out neoplastic, infectious, metabolic, toxin or other etiologic causes prior to labeling an AE as an irAE.

AESI including non-serious AESI should be reported via the SAE Report Form according to the timelines and contact details given in Section 10.3.1.10 of this protocol. For non-serious AESI, the seriousness criterion should not be reported/selected as these non-serious AESIs are to be reported according to the timelines of SAEs, but mostly do not have the seriousness of an SAE.

Page 86 of 133 Version: 7.0 Date: 09 FEB 2023

8.5 Treatment of overdose

For this trial, accidental or intentional overdose is defined as at least two times the intended dose of trial treatment within the intended therapeutic window, if associated with an AE.

In the event of an overdose, the investigator should:

- Contact the medical monitor immediately (within 24 h).
- Closely monitor the patient for any AE/SAE and laboratory abnormalities.
- Document the quantity of the excess dose as well as the duration of the overdose in the eCRF.

Decisions regarding dose interruptions or modifications will be made by the investigator in consultation with the medical monitor based on the clinical evaluation of the patient.

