- f "n" represents the number of the respective cycle (e.g., C4 means fourth cycle of treatment).
- g Visit CnD1 should occur 21 (± 3) d after the first day (i.e., treatment visit) of the previous cycle.
- h Informed consent must be documented before any trial-specific screening procedure is performed.
- i Eligibility should be confirmed and documented in the eCRF. This should be performed when all screening results are available and within 21 d after initiation of screening.
- j Underlying disease history should include histology, TNM stage at diagnosis (including which AJCC edition), prior anti-cancer therapies/procedures, date of last progression.
- k BRAF V600 mutation status may be obtained from medical history data.
- TNM staging at the time of trial entry to be performed according to AJCC 8th edition.
- m Concomitant medication and therapy includes any therapies (e.g., prescription drugs, over-the-counter drugs, vaccines, herbal or homeopathic remedies, nutritional supplements) used by a patient in addition to protocol-mandated trial treatment from 28 d prior to initiation of trial treatment until the SFU2 visit.
- n Vital signs (body temperature, pulse rate, respiratory rate, and blood pressure) should be measured within 60 min prior to the administration of the trial treatment(s) and at 30 (±10) min, 60 (±10) min, 4 h (±10 min), and 6 h (±10 min) after administration, or if clinically indicated (see Section 8.2.3 for guidelines on reduction or expansion of these time points).
- o At screening and at EoT assessments must include a full physical examination. Record abnormalities observed on the respective eCRF pages as appropriate. For all subsequent physical examinations perform a limited, symptom-directed examination at specified time points and as clinically indicated at other time points. Record new or worsened clinically significant abnormalities on the AE eCRF.
- p Single 12-lead ECG recordings will be obtained during screening, at EoT, and as clinically indicated at other time points. Patients should be resting in a supine position for ≥ 10 min prior to ECG recording. The interpretation of the ECG recording will be done locally by the investigator.

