- y Hematology assessment should be performed at screening, ≤ 24 h prior to each drug administration, on treatment discontinuation, and at 30 d SFU1 or if clinically indicated (see Section 10.2 for assessments to be done). Samples should be assessed by both the central and local laboratory. Results of local laboratory assessments need to be reviewed prior to drug administration. Unscheduled assessments can be performed locally, or sent to the central laboratory.
- z Serology assessments for patients will include HBsAG, anti-HBc, anti-HBs and anti-HCV. HIV (1/2) testing required if the patient has never been tested for HIV or if testing was prior to primary cancer diagnosis or performed ≥ 12 mon prior to trial start. Samples should be shipped to a central laboratory.
- aa Chemistry panel should be performed at screening, ≤ 24 h prior to each drug administration, on treatment discontinuation, and at 30 d SFU1 or if clinically indicated (see Section 10.2 for assessments to be done). Samples should be assessed by both the central and local laboratory. Results of local laboratory assessments need to be reviewed prior to drug administration. Unscheduled assessments can be performed locally, or sent to the central laboratory.
- bb Coagulation assessments to be performed at screening, at EoT and if clinically indicated (see Section 10.2 for assessments to be done). Samples should be shipped to a central laboratory; unscheduled assessments can be performed locally.
- cc TSH and free T4 will be assessed at screening, once every two cycles, on treatment discontinuation, at SFU1, and as clinically indicated. Samples should be shipped to a central laboratory and, if required, to the local laboratory. Unscheduled assessments can be performed locally, or sent to the central laboratory.
- dd All WOCBP will have a serum pregnancy test at screening, within 10 d prior to initiation of trial treatment. Urine or serum pregnancy test will be performed at the start of every cycle (starting from Cycle 2) or according to local requirements (in cases where more frequent testing is required) and at EoT and SFU1. If a urine pregnancy test is positive, hold dosing and confirm the result with a serum pregnancy test.
- ee For urinalysis assessments dipsticks are to be used, microscopic evaluation should be performed per investigator's discretion. Tests will be done locally with material provided by the central laboratory.

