2.3.1 Risk assessment

Expected adverse drug reactions (ADR) for BNT111 are fever, chills, lymphopenia, increase of cytokines and dizziness, not considered to have a significant impact on the risk-benefit profile of the product. NCI-CTCAE Grade 2 or 3 hypotension was seen in 8% of patients within 4 to 6 h after BNT111 administration, typically after the first or second vaccination, and patients with hypotension responded well to fluids. In rare cases, more severe events of cytokine release syndrome associated with pyrexia, hypotension, and hypoxia of higher NCI-CTCAE grades occurred. The onset was sometimes sudden; vital signs should therefore be carefully monitored for 6 h after at least the first three vaccinations.

Immune-related adverse reactions can occur with cemiplimab. Most of these, including severe reactions, resolved following initiation of appropriate medical therapy or withdrawal of cemiplimab. The most common immune-related adverse reactions seen in clinical trials (591 patients) were hypothyroidism (7.1%), pneumonitis (3.7%), immune-related skin adverse reactions (2.0%), hyperthyroidism (1.9%) and hepatitis (1.9%). Adverse reactions were serious in 8.6% patients and led to permanent discontinuation of cemiplimab in 5.8% of patients. See Section 6.8.4.2 for special warnings and precautions.

BNT111 has been given in combination with anti-PD-1 therapy in the Lipo-MERIT trial, no increase of AEs for any of the components was seen for the combination therapy compared to monotherapy. Safety data from the BNT111-01 trial interim analysis was in line with that observed in the Lipo-MERIT trial (Section 5.2 of the BNT111 IB). Based on the available safety data on TESAEs and treatment-emergent deaths, no safety signal was detected which would change the safety profile or benefit/risk assessment of BNT111 established in Lipo-MERIT trial. This was supported by the outcome of all IDMC meetings that recommended to continue the trial without modification.

Page 39 of 133 Version: 7.0 Date: 09 FEB 2023

Table 1: Summary of important, potential risks and mitigation actions taken

Potential risks	Actions taken	
General safety	An IDMC manages all potential safety concerns in this trial.	
Risks related to cancer vaccine antigen targets or anti-PD-1 therapy	Patients with clinically relevant autoimmune diseases are excluded from the trial.	

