10.3.1.9 Documentation of particular situations

AEs that are secondary to other events

In general, AEs that are secondary to other events (e.g., cascade events or clinical sequelae) should be identified by their primary cause, with the exception of severe or serious secondary events. A medically significant secondary AE that is separated in time from the initiating event should be documented as an independent AE in source data and eCRF. For example:

If vomiting results in mild dehydration with no additional treatment in a healthy adult, only vomiting should be documented as AE.

If vomiting results in severe dehydration, both events should be documented as AEs separately.

Abnormal laboratory results and vital signs values

Not every laboratory or vital signs abnormality needs to be documented as AE. For clinically significant laboratory/vital signs abnormalities the following definitions and documentation rules apply:

- If a laboratory/vital signs abnormality is a sign of a disease or syndrome, the laboratory/vital signs abnormality is clinically significant and only the diagnosis of the causing disease or syndrome needs to be documented as AE.
- If a laboratory/vital signs abnormality results in specific symptoms but no diagnosis of a disease or syndrome can be made, the laboratory/vital signs abnormality is clinically significant and only the symptoms need to be documented as AEs.
- If a laboratory/vital signs abnormality is not a sign of a disease or syndrome and does not result in specific symptoms but leads to a change in trial treatment or in a medical intervention, the laboratory/vital signs abnormality is clinically significant and must be documented as AE.

AEs associated with an overdose or error in drug administration

An overdose is the accidental or intentional use of a drug in an amount (per administration or cumulatively) higher than the dose being studied (for the trial treatment) or higher than the maximum recommended dose according to the authorized product information (for approved concomitant medications). An overdose or incorrect administration of a drug is not itself an AE, but it may result in an AE.

All AEs associated with an overdose or incorrect administration should be documented as AE in source data and eCRF and reported as SAE if applicable.

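### Protocol 8.5 counts a doubled dose as an overdose only when an AE accompanies it, so an AE-free dosing error triggers none of the section's three instructions

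*Protocol*

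**What the plan says.** Protocol 8.5 sets the definition for this trial. Overdose, whether by accident or on purpose, is there "defined as at least two times the intended dose of trial treatment within the intended therapeutic window, if associated with an AE". The AE is part of the definition itself, not a qualifier on reporting.

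The investigator's instructions in 8.5 apply in the event of an overdose so defined:

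- contact the medical monitor within 24 h;
- "Closely monitor the patient for any AE/SAE and laboratory abnormalities";
- record the excess quantity and the duration in the eCRF.

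Protocol 10.3.1.9 has a second definition: any amount above the dose being studied or, for approved concomitant drugs, above the maximum recommended dose. It has no two-fold threshold and no AE condition. It adds that "An overdose or incorrect administration of a drug is not itself an AE, but it may result in an AE". What it asks for is documentation of the AEs that go with the overdose, and SAE reporting where applicable. Protocol 10.3.1.1 states that overdose on its own is not reported as an AE or SAE.

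**The concern.** One purpose of an overdose rule is to set surveillance in motion before harm shows. Here close monitoring for AEs becomes an instruction only after an AE is present. A site that finds a doubled dose in a patient who is well has an overdose under 10.3.1.9 and none under 8.5, and 10.3.1.9 gives it nothing to do until an AE occurs.

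Being well when the error is noticed does not rule out a later event, even at intended doses. Protocol 2.3.1 describes Grade 2 or 3 hypotension "seen in 8% of patients within 4 to 6 h after BNT111 administration". On immune-related events, Protocol 8.4 says that "An irAE can occur shortly after the first dose or several months after the last dose of treatment". At stake is how promptly the medical monitor hears of the error and how closely the patient is watched between the error and any first AE. No efficacy estimate is at stake.

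**Working it through.** The plan gives no figure to reproduce. The check is whether the 8.5 actions are triggered, and whether any other text requires them.

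**Step 1, the trigger.** An 8.5 overdose requires (dose ≥ 2 × intended) AND (associated AE).

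- Dose ≥ 2 × intended, AE present: both conditions hold, so all 3 instructions apply.
- Dose ≥ 2 × intended, no AE: the second condition fails, so 0 of 3 apply under 8.5.
- With the AE condition deleted: 3 of 3 apply in both cases.

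This count only restates the definition. It does not measure clinical effect.

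**Step 2, cover elsewhere for an AE-free error.**

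| 8.5 action | Nearest other provision | What remains open |
|---|---|---|
| Contact within 24 h | Protocol 8: immediate safety concerns go to the medical monitor at once | Overdose is not named; the site must judge a well patient to be such a concern |
| Close monitoring | Protocol 8.3.1: AEs collected from consent to SFU2. SOA1 footnote n: vital signs before dosing and at 30 min, 60 min, 4 h and 6 h after | Routine schedule only; nothing is stepped up because of the excess dose |
| Entry of excess quantity and duration | Protocol 6.6: date and time of each dose recorded. SAP 8.5.1: actual cumulative dose is the sum of administered doses | Administered amounts are needed anyway, but no entry identifying the excess is required |

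Protocol 8.3.3 does not fill the gap. Its rule that "the investigator is required to proactively follow each patient at subsequent visits/contacts" starts from an initial AE or SAE report.

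**Step 3, where cover is thinnest.** Protocol 8.2.3 requires at least 6 h of observation after the first three BNT111 doses and the first cemiplimab dose. Section 2.3.1 places hypotension typically after the first or second vaccination, so its usual onset falls inside that mandatory period. Afterwards 2 to 4 h is acceptable following well-tolerated BNT111, at the investigator's discretion. From the second cemiplimab dose no observation time is stipulated. A 2 h observation ends before the 4 to 6 h window opens, and a 4 h observation ends as it opens.

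**Step 4, scheduled laboratory samples.** Hematology and chemistry are due up to 24 "h prior to each drug administration, on treatment discontinuation, and at 30 d SFU1 or if clinically indicated". In the three-weekly phase, "Visit CnD1 should occur 21 (± 3) d after the first day (i.e., treatment visit) of the previous cycle". The next scheduled sample after a dose therefore falls between:

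- earliest: 21 − 3 − 1 = 17 days;
- latest: 21 + 3 = 24 days.

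During weekly BNT111 dosing the interval is about a week. Either can be shortened if a sample is clinically indicated. Section 8.5 sets no laboratory date, so these figures describe the background schedule and are not something the fix would change.

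**The case against.** The strongest reply is that the literal gap is real but little follows from it. Several parts of that reply stand.

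- A reader might infer that nobody looks for AEs until one exists. The documents do not support that: AE collection and scheduled vital signs apply to every treated patient. Only the added instruction to monitor closely depends on the trigger.
- A reader might infer that 8.5 contradicts 10.3.1.9. It does not. Section 8.5 never calls an overdose an AE; the two sections differ in scope and purpose, one setting management and the other documentation.
- A reader might infer that the hypotension risk goes unobserved, or that patients go 17 to 24 days without laboratory tests. The first overlooks the mandatory early observation. The second holds only for scheduled samples in the three-weekly phase.
- A reader might infer that AE-free patients would gain most from the 8.5 monitoring. Nothing in the documents compares the benefit in the two groups.
- For BNT111 the affected group may be small. Section 8.5 sets no minimum AE grade, and flu-like reactions are anticipated (Protocol 6.8.4.1), so a mild reaction associated with the excess dose would bring 8.5 into play. This argument is specific to BNT111.

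The Pharmacy Manual, Medical Monitoring Plan and Safety Management Plan were not available and may contain dosing-error instructions. What does not stand is the claim that existing provisions replace 8.5: each is either routine or left to the site's judgment, and none explicitly requires its actions.

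**Conclusion.** The point holds as a narrow gap in a safety procedure. On the wording of 8.5, a two-fold or larger dose without an AE triggers none of the three instructions, and no other text in the protocol or SAP explicitly requires them. If an associated AE appears later, 8.5 applies from then. What is missing is prompt contact and closer monitoring in the interval before it, together with the excess-dose entry if no AE ever follows. The gap is widest for later doses.

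The number of patients cannot be estimated: no dosing-error rate is given and dose levels are redacted. The conclusion assumes that 8.5 is applied as written and that the unseen manuals do not already cover the case. A careful investigator may call the medical monitor anyway. The ORR analysis is unaffected. Priority is low and confidence medium.

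**What to change.** At the next amendment, delete the AE condition that closes the 8.5 definition (its last five words) and keep the two-fold threshold, which is the sponsor's choice. Leave 10.3.1.9 as the broader AE-documentation rule, which also covers concomitant drugs, and add a cross-reference there saying that 8.5 sets the management trigger. The two definitions will still differ in threshold, but their roles will be clear.

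The cost is one phrase, one cross-reference and a few more medical monitor contacts for AE-free errors of two-fold or more; the documents do not allow that number to be estimated. No analysis changes. The edit makes closer monitoring an instruction but does not set a date for laboratory tests.
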